6.1.7. Derived Variables

- Respiratory failure is defined as the requirement for use of intubation/mechanical ventilation, an oxygen rate with high flow nasal cannula greater than 20 L/min, non-invasive positive pressure respiratory support, or ECMO, or clinical diagnosis of respiratory failure.
- Respiratory failure-free survival is defined as the combination of no respiratory failure (defined above) and no report of mortality from any cause.
- Mortality from any cause is defined as death listed on the Study Completion CRF or WHO 9-point ordinal scale assessment of death.
- Non-invasive positive pressure respiratory support is defined as the use of continuous positive airway pressure (CPAP) or bilevel positive airway pressure (BiPAP).
- Ventilator use is defined as the use of mechanical ventilation, CPAP, or BiPAP.
- Organ failure is defined as a reported AE indicating a ‘failure’ of respiratory, cardiovascular, hepatic, renal, coagulation, or neurological reported at the PT level or

‘insufficiency’ reported as the lowest level term.

- Renal stabilization or replacement is defined as reported use of any type of dialysis in concomitant medications with a route recorded as (“HEMODIALYSIS”, “PERITONEAL DIALYSIS”, or “DIALYSIS”).
- Time to initiation of supplemental oxygen or other respiratory support in the first 28 days after randomization = (the earliest of Day 28 or date/time of the first use – date/time of randomization) + 1.
- Duration of supplemental oxygen or other respiratory support in the first 28 days after randomization = (the earliest of Day 28 of the study or date/time of the last use – the latest of date/time of the first supplemental oxygen or other respiratory support or date/time of randomization) + 1.
- Time to initiation of intubation/mechanical ventilation, an oxygen rate with high flow nasal cannula greater than 20 L/min, non-invasive positive pressure respiratory support, ECMO in the first 28 days after randomization = (the earliest of Day 28 or date/time of the first support – date/time of randomization) + 1.
- Duration of intubation/mechanical ventilation, an oxygen rate with high flow nasal cannula greater than 20 L/min, non-invasive positive pressure respiratory support, or ECMO in the first 28 days after randomization = (the earliest of Day 28 of the study or date/time of the last specified respiratory support – the latest of date/time of the first specified respiratory support or randomization) + 1.

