The number of days of supplemental oxygen or other respiratory support in patients not meeting the criteria for respiratory failure from randomization through Day 28 will be summarized descriptively and analyzed using ANCOVA. The LS means will be presented along with the associated 95% CI within each treatment group. In comparing treatments, LS mean differences between treatments will be presented along with associated 95% CIs and p-values. For Part 1 analysis, this endpoint will be reported in all patients in the ITT population.

The time to start of supplemental oxygen or other respiratory support from randomization through Day 28 will be analyzed using a Cox-Proportional hazard model. The number of participants who experience the event and rate ratio with 95% CI will be presented. The p-value to test if the rate ratio between treatments differs from 1 will be evaluated. Kaplan-Meier methodology will be used to estimate the median time to the event and 95% CI. Censoring events include loss to follow-up prior to Day 28. Mortality will not be considered a censoring event and instead will be analyzed as if this patient was on supplemental oxygen or other respiratory support for all days between randomization and Day 28. If mortality or the event of interest does not occur, all subjects will be censored at Day 28. Covariates will include those a priori specified in [Section 6.1.2](#), and Efron's method for handling tied time-to-events will be used. The p-value testing for non-zero treatment effect will be obtained from a Wald chi-square test, and the 95% CI associated with the treatment effect will be a Wald-type CI.

Duration and time to supplemental oxygen or other respiratory support through Day 28 will be calculated according to [Section 6.1.7](#)

8.2.5. Among patients that experience respiratory failure in the first 28 days, time to initiation and duration of the forms of respiratory support meeting criteria outlined in critical COVID criteria (exclusion criteria 1.c.i) within the first 28 days

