The number of days of respiratory support meeting criteria outlined in the critical COVID criteria among patients that experience respiratory failure in the first 28 days from randomization through Day 28 will be summarized descriptively and analyzed using ANCOVA. The LS means will be presented along with the associated 95% CI within each treatment group. In comparing treatments, LS mean differences between treatments will be presented along with associated 95% CIs and p-values.

For study Part 1 analysis, this endpoint will be reported in all patients in the ITT population.

The time to start of respiratory support through Day 28 will be analyzed using a Cox-Proportional hazard model. The number of participants who experience the event and rate ratio with 95% CI will be presented. The p-value to test if the rate ratio between treatments differs from 1 will be evaluated. Kaplan-Meier methodology will be used to estimate the median time to the event and 95% CI. Censoring events include loss to follow-up prior to Day 28. Mortality will not be considered a censoring event and instead will be analyzed as if the patient was on the forms of supplemental oxygen for all days between randomization and Day 28. If mortality or the event of interest does not occur, all subjects will be censored at Day 28. Covariates will include those a priori specified in [Section 6.1.2](#), and Efron's method for handling tied time-to-events will be used. The p-value testing for non-zero treatment effect will be obtained from a Wald chi-square test, and the 95% CI associated with the treatment effect will be a Wald-type CI.

Duration and time to the forms of respiratory support through Day 28 will be calculated according to [Section 6.1.7](#).

In order to assign the worst total score for death, participants that die will have all days from randomization through Day 28 treated as if they were receiving critical COVID-level respiratory support (i.e., analyzed as having 28 days of COVID-level respiratory support) for these analyses. Participants that do not die but have missing data will not be excluded from the analysis of duration or time-to-event endpoints and will have an appropriate value assigned.

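### SAP 6.1.7 derives the two support durations as a first-to-last span, while 8.2.4 and 8.2.5 analyse them as days on support, so support-free gaps are counted

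*SAP*

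**What the plan says.** SAP 6.1.7 (Derived Variables) defines two durations with the same structure. The first reads "Duration of supplemental oxygen or other respiratory support in the first 28 days after randomization = (the earliest of Day 28 of the study", continuing "or date/time of the last use – the latest of date/time of the first supplemental oxygen or other respiratory support or date/time of randomization", with 1 then added. The second covers intubation or mechanical ventilation, high-flow oxygen above the stated rate, non-invasive positive pressure support and ECMO. It ends "or date/time of the last specified respiratory support – the latest of date/time of the first specified respiratory support or randomization) + 1".

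SAP 8.2.4 names its analysed variable as "The number of days of supplemental oxygen or other respiratory support in patients not meeting the criteria for respiratory failure" and adds "Duration and time to supplemental oxygen or other respiratory support through Day 28 will be calculated according to" Section 6.1.7. SAP 8.2.5 does the same for the critical-level forms: the variable is "The number of days of respiratory support meeting criteria outlined in the critical COVID criteria among patients that experience respiratory failure", and "Duration and time to the forms of respiratory support through Day 28 will be calculated according to" Section 6.1.7. Both are summarised descriptively and analysed by ANCOVA.

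Three other provisions bear on the point:

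- SAP 8.2.5 scores participants who die as having 28 days of critical-level support. SAP 8.2.4 has a comparable death rule only in its Cox model paragraph.
- SAP 6.1.4 keeps participants without the event in the duration analyses and says a suitable value will be assigned, but gives no number.
- SAP section 10 drops the subsetting of both endpoints for Part 1, so they are reported in all Part 1 ITT participants.

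**The concern.** A first-to-last span and a count of days on support agree only when support is continuous. Someone weaned from oxygen, and perhaps discharged, who later needs it again has the whole interval off support counted as time on support. Nothing in the protocol or SAP subtracts gaps, sums episodes or defines an episode, and the death and missing-data rules do not deal with gaps.

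The reported means would therefore not be what 8.2.4 and 8.2.5 call them. The overstatement is largest in participants who recover for a long stretch before a second episode. SAP section 10 now plans summary statistics and confidence intervals for these endpoints in Part 1, where the arms are very small and one such participant can dominate an arm's mean.

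**Working it through.** **Inputs.** The formula comes from SAP 6.1.7, the variable names from 8.2.4 and 8.2.5, and the Part 1 allocation of 5:5:5:3 (18 participants) from SAP 3.1 and 3.2. The documents give no restart rate, gap length or expected duration, so there is no planned figure to reproduce.

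**Formula, in whole study days with randomization on Day 1.**

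Span = min(28, last use) − max(first use, 1) + 1.

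Count = number of distinct days from Day 1 to Day 28 with support.

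For a survivor, span − count = number of support-free days between first and last use.

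**Illustrative patterns (survivors).**

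| Days on support | Span under 6.1.7 | Days with support | Excess |
|---|---|---|---|
| 1–5 | 5 − 1 + 1 = 5 | 5 | 0 |
| 1–3 and 6–7 | 7 − 1 + 1 = 7 | 3 + 2 = 5 | 2 |
| 1–4 and 20–22 | 22 − 1 + 1 = 22 | 4 + 3 = 7 | 15 |
| 1–3 and 26–27 | 27 − 1 + 1 = 27 | 3 + 2 = 5 | 22 |
| 1 and 28 only | 28 − 1 + 1 = 28 | 2 | 26 (maximum) |

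If last use is not restricted to the first 28 days, support on Days 1–4 and again on Days 35–36 gives min(28, 36) − 1 + 1 = 28, against 4 days of support by Day 28.

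**Effect on an arm mean.** If a share q of an arm restarts after a mean gap of g days, the mean rises by q × g. With assumed ranges of q from 0.05 to 0.25 and g from 2 to 15 days, the rise runs from 0.05 × 2 = 0.1 to 0.25 × 15 = 3.75 days.

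**Effect on the treatment difference.** With a common gap g, the shift is (q on varespladib − q on placebo) × g. Equal shares give 0. Shares of 10% and 20% with a 5-day gap give (0.10 − 0.20) × 5 = −0.5 days.

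**Effect in Part 1, if summarised by arm.** One survivor with the Days 1–3 and 26–27 pattern moves the mean of a 5-person arm by 22 / 5 = 4.4 days, and of the 3-person placebo arm by 22 / 3 = 7.3 days.

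**Participants with no support.** Without subsetting, the critical-level duration must be given a value for Part 1 participants who never had that support. The formula needs a first and a last use, which they lack, and 6.1.4 supplies no number.

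**The case against.** The strongest reply is that the span may be intended. The endpoint lists (Protocol 13.1.4.1, SAP 2.2.1.2) say duration, 6.1.7 derives a duration, and a separate secondary endpoint already covers the number of days of oxygen support. This has force: against the endpoint lists alone, the span is a possible definition. It does not remove the mismatch, because 8.2.4 and 8.2.5 name the same variable as a number of days. Either the derivation or the label has to change, and relabelling is a legitimate alternative.

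It is also fair that the practical reach is limited. These are secondary endpoints in an exploratory study, Part 2 had one participant at the pause, and Part 1 efficacy will carry no hypothesis tests or P values. The restart rates and gaps above are assumptions, and the 22-day example is near the extreme.

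A reader might infer more than the documents support in four ways:

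- **That the added 1 is itself an error.** In whole days it is ordinary inclusive counting, and a count of days with any use also scores brief use as a full day.
- **That participants who never used support were forgotten.** SAP 6.1.4 keeps them in the analysis; only the number is missing.
- **That days of oxygen support, a key secondary endpoint in 8.1.1, is inflated too.** SAP 8.2.12 gives no derivation and does not refer to 6.1.7, so this cannot be said.
- **That the treatment comparison is biased.** It is biased only if restart frequency or gap length differs by arm. Equality cannot be assumed, but the documents do not show a difference either.

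**Conclusion.** The point holds as a mismatch between label and derivation in the two duration endpoints of SAP 8.2.4 and 8.2.5. The formula reading is certain: gaps count as days on support, with an excess of 0 for continuous support and at most 26 days. The size in an arm mean, 0.1 to 3.75 days, rests wholly on the assumed 5–25% restarting and 2–15 day gaps. Deaths scored at 28 days under 8.2.5 are unaffected by gaps. The primary endpoint is not affected, and the sample size was not based on a power calculation. The change is worth making because it is cheap and because a single participant can move a Part 1 arm mean by several days.

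**What to change.** In SAP 6.1.7, define both durations as the number of study days from randomization through Day 28 with any recorded qualifying support. Assign 0 to participants with none, which Part 1 needs because subsetting is dropped. Keep the 28-day assignment for deaths in 8.2.5, and state explicitly whether it also applies to the 8.2.4 duration and to deaths after Day 28, since 8.2.5 sets no time limit on death.

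State also how the 8.2.4 duration differs from days of oxygen support in 8.2.12, and give 8.2.12 its own derivation. Without subsetting, the two would otherwise be close to duplicates in Part 1.

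The cost is SAP wording and programming, provided interim stops and restarts are recorded. The documents do not show the oxygen data form. Protocol 10.3.1.1 says only that oxygen need is assessed throughout the study per institutional practice, although the ventilator-free and oxygen-day endpoints suggest that day-level data are expected. If stops and restarts are not captured, keep the formula and relabel the variable in 8.2.4 and 8.2.5 as time from first to last use. For Part 1 the wording should be settled before database lock. For Part 2 it fits the protocol and SAP amendment that SAP section 10 already announces for these endpoints.

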### 10.1. Study Duration

The overall study duration is expected to be approximately 18 months (6 months of active enrollment and 2 months of follow-up in Part 1; 2 to 4 weeks for DSMB review of Part 1 results at Day 28 and selection of the Part 2 dose; 6 months of active enrollment in Part 2; and 2 months of follow-up in Part 2).

The sequence and approximate duration of the study periods will be as follows:

1. Screening: up to 72 hours
2. Treatment: 7 days
3. Follow-up: 28 days after randomization
4. Safety follow-up: 45 and 60 days after randomization

The maximum study duration for each participant is approximately 60 days.

The treatment duration for each participant is 7 days from the point of randomization (7 complete days of study drug administration after randomization). Screening/enrollment and baseline (Day 1) of the Treatment Period can take place on the same day if the required screening test results are available.

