6.1. Statistical Definitions and Algorithms

6.1.1. Baseline

The last observation recorded before the first administration of IP will be used as the baseline observation for all calculations of change from baseline.

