- For the time till all-cause mortality Cox proportional hazards model, time to all-cause mortality or censoring will be calculated as follows
 - If mortality occurs within 60 days post-randomization; then Time to all-cause mortality or censoring = date/time of death – date/time baseline + 1.
 - If mortality occurs on or after 60 days post-randomization; then Time to all-cause mortality or censoring = 60 days.
 - If mortality does not occur, and last follow-up is prior to 60 days; then Time to all-cause mortality or censoring = date/time of last follow-up – date/time baseline + 1.
 - If mortality does not occur, and last follow-up is on or after 60 days; then Time to all-cause mortality or censoring = 60 days.
- Change from baseline = value at current time point – value at baseline.
- TEAE = any adverse event with an onset or worsening date/time after the date/time of the first administration of IP and prior to the 30 days after last dose of IP.

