8.2.2. All-Cause Mortality

All-cause mortality from randomization through Day 60 will be analyzed using a Cox-Proportional hazard model. The number of participants who experience the event and rate ratio with 95% CI will be presented. The p-value to test if the rate ratio between treatments differs from 1 will be evaluated. Kaplan-Meier methodology will be used to estimate the median time to the event and 95% CI. Time to all-cause mortality will be calculated according to [Section 6.1.7](#).

Censoring events include loss to follow-up prior to Day 60. Covariates will include those a priori specified in [Section 6.1.2](#), and Efron's method for handling tied time-to-events will be used. The p-value testing for non-zero treatment effect will be obtained from a Wald chi-square test, and

the 95% CI associated with the treatment effect will be a Wald-type CI.

Additionally, the proportion of participants who die will be analyzed using the same logistic regression and risk difference method with dummy coding as the primary endpoint (Ge et al, 2011). In general, the proportions of participants with an event on or before Day 60 will be analyzed.

8.2.3 Proportion of participants who experienced respiratory failure within the first 28 days after randomization

The proportion of participants experiencing respiratory failure from randomization through Day 28 will be analyzed using the same logistic regression and risk difference method with dummy coding as the primary endpoint. Respiratory failure is defined as defined by requiring HFNC >20 L/min, non-invasive positive pressure ventilation, mechanical ventilation, or ECMO, or clinical diagnosis of respiratory failure (exclusion criteria 1.c.i) at any time during the 28 days after randomization. Note that those who experience mortality after respiratory failure are still counted towards this analysis. Those who experience mortality without prior respiratory failure will not be counted towards this analysis.

8.2.4 Among patients that do not experience respiratory failure in the first 28 days, time to initiation and duration of supplemental oxygen or other respiratory support within the first 28 days

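### SAP 6.1.7 puts mortality times on two clocks, so late times can be mis-ordered and a death at or after day 60 has no stated event status

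*SAP*

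**What the plan says.** SAP 6.1.7 gives four branches for the time used in the mortality Cox model.

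- Death before 60 days: "If mortality occurs within 60 days post-randomization; then Time to all-cause mortality or censoring = date/time of death – date/time baseline + 1".
- Death at or after 60 days: "If mortality occurs on or after 60 days post-randomization; then Time to all-cause mortality or censoring = 60 days".
- Survivor lost earlier: "last follow-up is prior to 60 days; then Time to all-cause mortality or censoring = date/time of last follow-up – date/time baseline + 1".
- Survivor followed long enough: "If mortality does not occur, and last follow-up is on or after 60 days; then Time to all-cause mortality or censoring = 60 days".

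SAP 8.2.2 describes the analysis as "All-cause mortality from randomization through Day 60". It uses Efron's method for ties and names loss to follow-up before Day 60 as censoring. It reports the number of events beside the rate ratio and adds a logistic analysis of deaths on or before Day 60. The time-to-support variables elsewhere in 6.1.7 start at randomization.

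On the origin, SAP 6.1.1 says: "The last observation recorded before the first administration of IP will be used as the baseline observation". That definition is given for change-from-baseline calculations. Protocol 10.1 treats Day 1 as baseline ("Screening/enrollment and baseline (Day 1) of the Treatment Period can take place on the same day") and also allows "Screening: up to 72 hours".

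**The concern.** The death branches are chosen by days since randomization, but times short of 60 days are counted from baseline with a day added. The value at the cap carries neither the shift nor the extra day. A participant just short of day 60 can therefore receive a longer time than one followed past it.

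The Cox estimate uses only the order of the times. A death placed after everyone else has nobody left at risk to be compared with, so it contributes no information at its own event time. It would still appear in the event count printed beside the hazard ratio, and the two could disagree.

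Two further gaps sit in the same rule. It does not say whether a death on or after day 60 is an event or is censored at 60, and a death at exactly 60 days fits two branches. Baseline is also not a single timestamp: it is defined per variable as the last pre-dose observation, so two programmers could derive different survival times.

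**Working it through.** The documents give no hazard ratio, event count or power for mortality (SAP 3.2 states that the size has no formal power basis), so there is no figure to reproduce. The check applies the four branches directly.

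**Inputs**
- e = days from randomization to death or last contact. The survivor branches name no origin for their 60 days; they are read here as days from randomization, as the death branches state.
- L = days from baseline to randomization, assumed to be 0 to 3. The low end follows Protocol 10.1 (Day 1 is baseline); the high end is the 72-hour screening limit, 72/24 = 3.
- Final visit at Day 60 with a window of 4 days either side (Protocol 10.2.3.7), so last contact from 56 to 64 days.
- Part 2: 72 participants at 1:1, so 36 per arm (SAP 3.2).

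**Rule:** if e < 60, time = e + L + 1; if e ≥ 60, time = 60.

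**Step 1. Deaths timed above 60.** e + L + 1 > 60 means e > 59 − L.

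| L | Date/time values | Width | Whole dates displaced |
|---|---|---|---|
| 0 | 59 < e < 60 | 1 day | none (59 + 0 + 1 = 60, a tie) |
| 1 | 58 < e < 60 | 2 days | 59 |
| 2 | 57 < e < 60 | 3 days | 58, 59 |
| 3 | 56 < e < 60 | 4 days | 57, 58, 59 |

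Example with L = 0: 59.5 + 0 + 1 = 60.5.

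**Step 2. Survivors.** A survivor last seen at e = 59 gets 60, 61, 62 or 63 for L = 0, 1, 2, 3. At e = 58 with L = 3 the value is 58 + 3 + 1 = 62. A survivor seen at e = 64 gets 60. Late deaths therefore exceed the capped survivors, but not necessarily all survivors.

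**Step 3. Effect on the Cox estimate.** A shift common to everyone would leave the order, and so the hazard ratio (HR), unchanged; the harm comes from the unshifted cap. The illustration uses assumed data, 36 v 36: deaths at days 5, 12 and 20 on varespladib, at days 4, 8, 11, 17 and 25 on placebo, and one late death at e = 58.5. The model has treatment only, with Efron ties. SE is for the log HR. Without the late death, HR = 0.582 (SE 0.730). Results for L = 1 and L = 3 are the same:

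| Survivors' last contact | Late death on | SAP rule HR (SE) | One clock HR (SE) | Others at risk under SAP rule |
|---|---|---|---|---|
| All at day 60 or later | varespladib | 0.582 (0.730) | 0.774 (0.671) | 0 |
| All at day 60 or later | placebo | 0.582 (0.730) | 0.484 (0.707) | 0 |
| Spread over days 56 to 64 | varespladib | 0.760 (0.671) | 0.772 (0.671) | 8 |
| Spread over days 56 to 64 | placebo | 0.499 (0.708) | 0.485 (0.707) | 8 |

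In the first two rows the late death leaves the estimate where it was without it, although nine events are counted. In the last two it still counts, against 8 others. With L = 0 this death gets 58.5 + 0 + 1 = 59.5 and the two clocks agree.

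**Step 4. How often.** If deaths were uniform over 60 days (assumption), the share in the window is 1/60 = 1.7% to 4/60 = 6.7%. At an assumed mortality of 10% to 30% among 72: 72 × 0.10 × 1/60 = 0.12 and 72 × 0.30 × 4/60 = 1.44 deaths.

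**Step 5. The boundary.** A death at exactly 60 days gets 60 + L + 1 = 61 to 64 under the first branch and 60 under the second.

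**The case against.** A reader might infer that late deaths fall beyond every survivor and always drop out of the Cox model. The documents do not support that. The third branch gives survivors last seen before day 60 the same uncapped shift, and the final-visit window allows completers to be seen from day 56. A late death loses its contribution only if nobody else has a time as long. Even then, the person counts in every earlier risk set.

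A reader might also take 4 days as the settled width. It needs a 3-day lag. SAP 6.1.1 fixes an observation for each variable, not an origin for survival time, and the protocol calls Day 1 baseline. Day 1 vital signs are listed after randomization and before dosing (Protocol 10.2.2.1), so the lag can be about zero. With whole dates and a Day 1 baseline, no death is displaced. This stands, although SAP 6.1.7 specifies date/time values.

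On event status, SAP 8.2.2 limits the analysis to Day 60 and its proportions to deaths by then, which suggests that later deaths are not events. That helps, but neither section says so for the Cox model, whereas SAP 8.2.4 and 8.2.5 do state censoring at Day 28.

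Finally, consequences are limited. Under SAP 10, Part 2 paused with one participant, and Part 1 efficacy is reported without tests or P values. The logistic analysis of mortality does not use this clock, and the study is exploratory throughout.

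**Conclusion.** The point holds as a minor correction to a stated rule. SAP 6.1.7 mixes a baseline-plus-1 clock with an unshifted cap of 60, conflicts with the randomization origin in 8.2.2, and leaves the status of a death on or after day 60 undefined.

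The number of days affected depends on assumptions: the last day before day 60 with date/time values and no lag, up to the last 4 days with a 3-day lag, and none with whole dates and a Day 1 baseline. The loss of a late death from the hazard ratio is conditional on no other time being as long. Under even timing of deaths and 10% to 30% mortality, about 0.1 to 1.4 deaths in a full Part 2 would fall in the window. One such death can move the estimate visibly, as the illustration shows, but only in the less favourable follow-up pattern. The issue matters mainly if Part 2 resumes or the rule is reused.

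**What to change.** Replace the four branches with one rule for everyone, using calendar dates and counting the randomization date as Day 1:

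- study day = date of death or last contact − date of randomization + 1;
- time = min(study day, 60);
- event = 1 only if death occurs on study day 60 or earlier; otherwise censored at that time.

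A death 59 calendar days after randomization is then study day 60 and an event. One at 60 calendar days is study day 61 and is censored at 60. Add a sentence to SAP 8.2.2 applying the same Day 60 cut-off to the event count and the logistic analysis.

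The cost is one rewritten bullet in 6.1.7 and one sentence in 8.2.2, with no new data. SAP 10 already foresees an amendment for Part 2, which could carry the change.
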